 5 • Determine and compare TG concentration before and after the intervention with fucoxanthin and
 6 placebo.
 7 • Determine and compare HDL-c concentration before and after the intervention with fucoxanthin and
 8 placebo.
 9 • Determine and compare fasting serum glucose level before and after the intervention with
 10 fucoxanthin and placebo.
 11 • Determine and compare insulin sensitivity before and after the intervention with fucoxanthin and
 12 placebo.
 13 • Determine and compare the total secretion of insulin before and after the intervention with
 14 fucoxanthin and placebo.
 15 • Determine and compare the first phase of insulin secretion before and after the intervention with
 16 fucoxanthin and placebo.

17 **Secondary objectives**

18 • Determine and compare body weight before and after the intervention with fucoxanthin and placebo.
 19 • Determine and compare BMI before and after the intervention with fucoxanthin and placebo.
 20 • Determine and compare body fat percentage before and after the intervention with fucoxanthin and
 21 placebo.
 22 • Determine and compare insulin concentration before and after the intervention with fucoxanthin and
 23 placebo.
 24 • Determine and compare post-load glucose concentration after oral administration of 75 g of glucose
 25 before and after the intervention with fucoxanthin and placebo.
 26 • Determine and compare total cholesterol (TC), LDL cholesterol (LDL-c), and VLDL before and after
 27 the intervention with fucoxanthin and placebo.
 28 • Determine and compare AST and ALT levels before and after the intervention with fucoxanthin and
 29 placebo.
 30 • Determine and compare creatinine and uric acid levels before and after the intervention with
 31 fucoxanthin and placebo.
 32 • Describe the tolerability of treatment with fucoxanthin and placebo.

34 **MATERIALS AND METHODS**

35 **Design**

36 Randomized, double-blind, and placebo controlled clinical trial.

37 **Universe**

38 Men and women aged 30 to 60 with a diagnosis of MeS, residing in the metropolitan area of Guadalajara.

39 **Sample**

40 The sample size was calculated using a formula for the difference in means in clinical trials. A confidence
 41 level of 95%, a power of 80%, the standard deviation, and the expected difference obtained from the response
 42 variables in patients with metabolic syndrome were considered.

$$43 n = 2 \left(\frac{(Z_\alpha - Z_{1-\beta})(\sigma)}{\delta} \right)^2$$

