44 • Z_α corresponds to the value of statistical confidence, which was pre-set at a 95% confidence level,
 45 for a type I error of 5% expressed as a two-tailed α value of 0.05. For this confidence level, the Z
 46 value was 1.96.

- 1 • $Z\beta$ represents the statistical power and was pre-set at the $Z_{1-\beta}$ value of 80% for a type II error of
2 20%, which corresponds to a β value of 0.20. For this statistical power, the standardized Z score was
3 0.842.
- 4 • σ is the standard deviation of waist circumference (WC), insulin sensitivity, and insulin secretion in
5 patients with MetS.
- 6 • δ is the expected difference in waist circumference, insulin sensitivity, and insulin secretion in
7 patients with MetS.

8 A total of 28 patients, 14 for each study group, was the result obtained with the highest number of required
9 patients, including an additional 20% to anticipate possible loss to follow-up.

10 **Criteria**

11 Inclusion criteria

- 12 • Age between 30 and 60 years
- 13 • Diagnosis of metabolic syndrome (MetS) according to the IDF criteria:
 - 14 ○ Waist circumference (WC) \geq 80 cm in women or \geq 90 cm in men, plus two or more of the
15 following elements:
 - 16 ▪ Systolic blood pressure (SBP) \geq 130 mmHg and/or diastolic blood pressure (DBP) \geq
17 85 mmHg
 - 18 ▪ Triglycerides (TG) \geq 150 mg/dL
 - 19 ▪ HDL cholesterol (C-HDL) $<$ 40 mg/dL in men or $<$ 50 mg/dL in women
 - 20 ▪ Fasting plasma glucose (FPG) \geq 100 mg/dL
 - 21 • BMI between 25.0 and 34.9 kg/m²
 - 22 • No pharmacological treatment for the components of MetS
 - 23 • Stable weight during the last three months (weight variation less than 10%)
 - 24 • Female participants declared the use of a contraceptive method to prevent pregnancy during the study
25 period
 - 26 • Signed written informed consent form

27 Exclusion criteria

- 28 • Women who are pregnant or breastfeeding
- 29 • History of kidney, thyroid, or liver disease
- 30 • Consumption of medications or supplements with proven properties that modify the behavior of
31 metabolic syndrome
- 32 • Glucose \geq 126 mg/dL or diagnosis of type 2 diabetes mellitus
- 33 • Total cholesterol (TC) $>$ 240 mg/dL
- 34 • Triglycerides (TG) $>$ 500 mg/dL

35 Elimination criteria

- 36 • Non-compliance of medication intake exceeding 20%
- 37 • Intolerance to any of the intervention ingredients
- 38 • Meeting an exclusion criterion during the study
- 39 • Experiencing a serious adverse event
- 40 • Withdrawal of consent

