43 **Outcome measures**

44 *Primary outcome measures*

- 45 • WC
- 46 • DBP
- 47 • SBP
- 48 • TG
- 49 • HDL-c
- 50 • Glucose
- 51 • Insulin sensitivity

- First-phase insulin secretion
- Total insulin secretion

Secondary outcome measures

- Body weight
- BMI (Body Mass Index)
- Body fat percentage
- Lipid profile (Total cholesterol, LDL-c, VLDL)
- Post-load glucose
- Insulin levels
- Liver enzymes (ALT, AST)
- Creatinine levels
- Adverse events

Measurement and evaluation procedures

Demographic determinations

- Age: Expressed in completed years at the start of the intervention.
- Sex: Referring to the phenotypic sex at birth, it was recorded as male or female.

Clinical determinations

- *WC*: It will be measured using a flexible measuring tape with the subject standing. The tape was placed parallel to the ground and without clothing at the measurement level. The tape was positioned at the midpoint between the costal margin and the iliac crests at the end of a normal exhalation.
- *Weight*: It will be measured with the participant standing in a bipedal position, wearing light clothing, without shoes, and with an empty bladder prior to measurement. A stationary bioelectrical impedance scale will be used.
- *BMI*: It will be obtained by calculating the ratio of body weight in kg to the square of height in meters.
- *Body Fat*: It was determined using scale that utilizes the bioelectrical impedance method. Through a low-frequency signal, it calculates body fat and body composition.
- *SBP/DBP* (Systolic Blood Pressure/Diastolic Blood Pressure): It was determined using a digital sphygmomanometer. The participant was in a seated position after at least 5 minutes of rest. The cuff will be placed 3 cm above the elbow fold of the left arm. Two measurements will be taken to obtain the average blood pressure.

Clinical laboratory procedures

Oral Glucose Tolerance Test (OGTT)

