During each visit throughout the intervention, the patient will be interviewed and physically examined, if necessary, in search of changes in health status that may be related to the consumption of the formulation's ingredients.

Grupos de estudio y administración de la intervención

Two groups of 14 patients each will be formed:

- Fucoxanthin: Each patient will receive a capsule containing 12 mg of fucoxanthin every 24 hours. They will ask to take one capsule with the first bite of breakfast for a duration of 12 weeks.
- Placebo: Each patient will receive a placebo capsule (Magnesium stearate) that is indistinguishable from fucoxanthin. They will be instructed to take one capsule with the first bite of breakfast for a duration of 12 weeks.

Allocation of intervention and blinding

The treatment assignment will be performed through simple randomization, using the method of a simple random number table. By using computer software, each intervention will be randomly assigned an identification with a numerical code corresponding to an identified intervention within Group A or Group B. The patient and the researcher will not be informed of which pharmacological intervention corresponds to each numerical code.

DATA COLLECTION AND STATISTICAL ANÁLISIS PLAN

All the results will be collected in a digital database designed for this study, where no confidential personal information not related to the study variables will be recorded. The information entered in the database will be transferred for analysis in the statistical software IBM SPSS Statistics® for Windows®. The statistical analysis will be conducted at the end of the total data collection once the intervention in the included patients has finished. All patients will be included in the intention-to-treat analysis. In descriptive statistics, measures of central tendency and dispersion will be used. Quantitative variables will be presented with means and standard deviations. Qualitative variables will be presented with frequencies and percentages.

The Shapiro-Wilk test will be performed to determine the normality of the sample distribution in each variable. If the sample distribution is found to be abnormal, non-parametric tests will be used. The analysis between groups (independent samples) will be analyzed using the Mann-Whitney U test for quantitative variables, and the X² test or Fisher's exact test for qualitative variables. Intragroup analysis (two related

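### The elimination rule carries the glucose, TC and TG limits past randomisation, so as written it either does nothing or removes patients on their own outcome, against the intention-to-treat statement

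*Combined protocol and SAP*

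**What the plan says.** The Criteria section lists "Meeting an exclusion criterion during the study" as grounds for elimination and exempts no criterion. Three exclusion criteria are laboratory limits: glucose at or above "126 mg/dL or diagnosis of type 2 diabetes mellitus", TC above 240 mg/dL and TG above 500 mg/dL.

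Under Outcome measures, glucose and TG are among the nine items headed "Primary outcome measures"; TC is secondary. The objectives give the only timing: "Determine and compare fasting serum glucose level before and after the intervention with" each treatment, likewise "Determine and compare TG concentration before and after the intervention with fucoxanthin and" placebo, and the same for TC. Treatment lasts 12 weeks. The sections on adherence and adverse events describe visits during treatment (capsule return, interview, examination if needed) and name no blood test there.

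The statistical analysis plan says: "All patients will be included in the intention-to-treat analysis". Nothing defines whether elimination means stopping capsules, ending follow-up or removing data, or which statement prevails.

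**The concern.** Screening limits protect eligibility. Applied after randomisation to a variable that is also an outcome, they become a selection rule on the result. If no interim blood is drawn, a patient can newly exceed a limit only in the sample taken after the last capsule. No treatment is left to stop by then, so the only thing that can still be eliminated is the patient's data.

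If elimination prevails over intention to treat, high values leave both arms, and more of them leave the arm with the higher glucose. The estimated difference then shrinks towards zero. The loss is larger if fucoxanthin raises glucose, because patients reaching diabetic-range values on active treatment are the ones removed. Each removal would also take that patient's other primary outcomes out of an arm of 14.

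**Working it through.** **The text.** The contradiction needs no arithmetic. The rule covers all exclusion criteria, three of those are limits on outcomes, and the outcomes are timed before and after treatment. The analysis sentence keeps everyone.

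**The plan's own figure.** The plan states 14 per arm including 20% for loss. It gives no numerical SD or difference, so this cannot be recomputed from its inputs. Working back, 11 is the only whole number that gives 14 (11 × 1.2 = 13.2 and 11 / 0.8 = 13.75, both rounded up). The allowance is therefore 3 patients per arm.

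**How many would cross.** The limits and the 28 patients come from the protocol. Every mean and SD below is assumed, and the glucose limit is read as fasting. The usual level is N(μ, sb), and each measurement adds N(0, sw). A patient is eligible if the baseline value is within the limit, and crosses if the week-12 value is beyond it. With s = √(sb² + sw²), r = sb²/s² and z = (limit − μ)/s, the crossing share is 1 − Φ₂(z, z; r)/Φ(z). TG is modelled on the log scale (median shown).

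| | Setting 1 | Setting 2 | Setting 3 | Setting 4 |
|---|---|---|---|---|
| Glucose (μ, sb, sw) | 95, 10, 5 | 100, 10, 6 | 105, 10, 6 | 110, 10, 7 |
| TC (μ, sb, sw) | 185, 30, 11 | 195, 30, 12 | 205, 30, 14 | 210, 30, 15 |
| TG (median, sb, sw) | 170, .35, .20 | 200, .35, .20 | 200, .35, .20 | 230, .40, .22 |
| Glucose share | .0019 | .0089 | .0225 | .0590 |
| TC share | .0180 | .0341 | .0635 | .0831 |
| TG share | .0027 | .0078 | .0078 | .0257 |
| Any limit, q | .0226 | .0502 | .0917 | .1594 |
| Expected of 28 | 0.63 | 1.41 | 2.57 | 4.46 |
| At least one of 28 | 47% | 76% | 93% | 99% |

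The three limits are combined as independent. In setting 2, q = 1 − .9911 × .9659 × .9922 = .0502, and 28 × .0502 = 1.41. TC is the limit crossed most often: .0180/.0226 is about 80% of crossing patients in setting 1, and .0831/.1594 is about half in setting 4. For glucose or TG alone, the chance of at least one crossing is 12%, 38%, 58% and 91%.

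**Effect on the glucose difference.** Patients with week-12 glucose at or above 126 are removed in the same model (large simulation). The plan does not say whether arms are compared on final values or on changes, so both are shown.

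| True difference, mg/dL | Setting 1 | Setting 2 | Setting 3 | Setting 4 |
|---|---|---|---|---|
| −10, week-12 values | −9.94 | −9.75 | −9.45 | −8.81 |
| −10, change | −9.98 | −9.91 | −9.77 | −9.36 |
| +10, week-12 values | 9.35 | 8.53 | 7.60 | 6.46 |
| +10, change | 9.86 | 9.54 | 9.17 | 8.38 |

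As shrinkage, a benefit of 10 loses 0.06/10 to 1.19/10, about 1% to 12% (0% to 6% on change). A rise of 10 loses 0.65/10 to 3.54/10, about 7% to 35% (1% to 16% on change). With +10, the shares removed from the fucoxanthin arm are .028, .076, .149 and .259; from placebo they are the glucose shares above.

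**A second set of assumptions.** Baseline SD 10, SD of change 8 to 12, means 95 to 110 and a true difference of 5. On week-12 values, −5 becomes −4.84 to −3.58 and +5 becomes +4.62 to +3.07 (3% to 39% overall). On change, −5 becomes −4.94 to −4.07 and +5 becomes +4.85 to +3.77 (1% to 25%). The direction is the same and the size depends on the spread assumed.

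**Type I error.** With no effect, both arms lose patients by the same rule from the same distribution. The retained values still have equal distributions, so the test keeps its level.

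**The case against.** The strongest reply is that the analysis plan already settles the matter. It has one sentence on the analysis set, and that sentence includes everyone. The elimination list also contains intolerance, serious adverse events and withdrawal of consent, so it reads naturally as a list of reasons to discontinue. On that reading the laboratory limits are merely idle at week 12. This largely stands: the harmful branch is possible, not established. What remains is that the plan never says so, and the choice would fall to whoever handles the data once final values are known.

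Second, the absence of interim blood tests is inferred, because no visit schedule is supplied. If such tests exist, stopping capsules at a diabetic glucose value would be an ordinary safety measure, and the week-12 figures would not apply directly. Dropping the patient's data would still depend on an outcome variable.

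Third, the size is modest. Every population value is assumed, setting 4 describes a group with high glucose, and the most frequent crossing is on a secondary outcome. Change from baseline is affected much less. The cited human work gives no glucose-raising effect, although the Rationale calls the findings on glucose inconsistent. All of this stands and limits the weight of the point.

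A reader might infer that the trial will discard patients, or that false positives would rise. The documents do not say the first, and the argument above rules out the second. Nor does the point extend to the other exclusion criteria. Pregnancy, new medication or a diabetes diagnosis made outside the trial can arise mid-study, and there the rule has a real function.

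**Conclusion.** The point holds for the three laboratory limits. On the only timing stated, that part of the rule is either without effect or selects patients on a primary or secondary outcome, contrary to the intention-to-treat sentence. This rests on the text, with the single inference that no interim blood is drawn.

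The consequence is conditional on elimination prevailing and on assumed population values. In the hypothesised direction the distortion is small in most settings; it is larger for a glucose rise. The glucose figures cover removal on glucose alone, not on TC or TG. This merits a clarification at the level of something to consider.

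**What to change.** Under Elimination criteria, add: *The glucose, TC and TG limits apply for eligibility only. After randomisation a crossing is recorded, the patient is referred for care and capsules may be stopped for safety, but measured results are not removed.*

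In the statistical analysis plan, add: *No patient's collected outcome data are removed because a laboratory limit was crossed. The number crossing each limit is reported by group.*

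The cost is these few sentences and one table row per limit, with no added visit, test or patient. Handling of the other elimination criteria is unchanged. The downside is that patients who start glucose- or lipid-lowering drugs after referral stay in the analysis and may slightly dilute a difference. A supportive analysis without them, labelled as such, can be added.

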Metabolic syndrome (MetS) is a clinical condition with a multifactorial etiology and is a significant contributor to the development of atherosclerotic disease, T2DM, kidney disease, and other vascular complications.

As urbanization, food industrialization, sedentary lifestyles, and poor diets become more prevalent in the global population, mortality rates from MetS-related diseases are increasing, particularly in Western countries compared to the Eastern region. This discrepancy is associated with the daily consumption of marine algae, which are rich in nutrients and bioactive agents, in traditional Asian cuisine.

The initial treatment approach for MetS focuses on modifying risk factors such as obesity, physical inactivity, and unhealthy diets through lifestyle changes. While pharmacological treatments are available to control individual components of MetS, there is significant interest in developing new therapeutic approaches that target multiple components simultaneously, aiming to improve the cost-effectiveness and overall efficacy of treatment.

Fucoxanthin, a functional compound found in various species of marine algae traditional medicine. It has gained attention due to its beneficial effects on obesity, diabetes, and cancer. Animal studies have provided insights into its mechanism of action and safety; however, human research in this area is limited, and more studies are needed to establish the actual benefits of its consumption. The available information suggests favorable effects on weight control in overweight individuals, but its impact on glucose levels, lipid metabolism, and blood pressure appears inconsistent. Therefore, it is crucial to investigate the effects of fucoxanthin administration in patients with MetS.

Fucoxanthin represents an alternative worth studying, as it has shown anti-obesity, anti-diabetic, and antioxidant effects. It presents a natural and promising option for MetS therapy, but further research is required to establish its safety and effectiveness in this context.

HIPÓTESIS

Fucoxanthin modifies components of the metabolic syndrome, insulin sensitivity, and insulin secretion.

OBJECTIVE

To evaluate the effect of fucoxanthin on metabolic syndrome, insulin sensitivity and insulin secretion.

1 **Specific objectives**

2 • Determine and compare WC before and after the intervention with fucoxanthin and placebo.
 3 • Determine and compare SBP and DBP before and after the intervention with fucoxanthin and
 4 placebo.

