1 samples) will be performed using the Wilcoxon rank test for quantitative variables. A value of $p \leq 0.05$ will
2 be considered statistically significant.

3
4 **ETHICAL CONSIDERATIONS**

5 The project of this study was submitted for evaluation by the Research Ethics Committee of the University
6 Center of Health Sciences of the University of Guadalajara. The approval of this committee was obtained in
7 the record registered with the number CIE/467/2018. This study is classified as a study with greater than
8 minimal risk, for which the voluntary signature of an informed consent was requested from each participant,
9 in accordance with the Regulations of the General Health Law on Research for Health, in its Second Title,
10 chapter I, article 17. In accordance with the guidelines of good clinical practice, all study participants were
11 uniquely identified by alphanumeric code in a digital database. The data is kept confidential, as are the
12 answers to the questionnaires and the results of the clinical and laboratory tests, to guarantee the privacy of
13 the participants.

14 The procedures adhered to ethical standards, and strict respect was maintained for the individual integrity of
15 each participant. In accordance with the Regulations of the General Health Law on Research and the
16 principles emanating from the 18th Medical Assembly of Helsinki, Finland in 1964 and the modifications
17 made by said Assembly in Tokyo, Japan in 1975, in Venice, Italy in 1983, in Hong Kong in 1989 and the
18 64th General Assembly, Fortaleza, Brazil, October 2013, where medical research (clinical research) is
19 contemplated.

20
21 **FOUNDING INFORMATION**

22 Founding in this project is parallel to other studies of the University of Guadalajara.

23
24 **AUTHORS DISCLOSURE STATEMENT**

25 The researchers and personnel involved in conducting this study declare that they have no conflicts of
26 interest.

27
28 **REFERENCES**

- 30 1. Lim S, Eckel RH. Pharmacological treatment and therapeutic perspectives of metabolic syndrome. Rev Endocr Metab Disord 2014;15:329-41.
- 31 2. Báez-Duarte BG, Zamora-Ginez I, Cortés-Romero C, et al. Sensibilidad a La Insulina Y Síndrome Metabólico. RCAN Rev Cubana Aliment Nutr 2014;24:140-9.
- 32 3. Alberti G, Zimmet P, Shaw J, et al. The metabolic syndrome—a new worldwide definition. The Lancet 2005;366:1059-62.

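### Nine unranked primary outcomes are each tested at p ≤ 0.05 with no success rule; if any one counts as support, the false-positive risk is 27–37% at assumed correlations of 0.5 to 0

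*Combined protocol and SAP*

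**What the plan says.** - **Outcomes.** Under "Primary outcome measures", the Outcome measures section lists nine items: waist circumference (WC), diastolic pressure, systolic pressure, triglycerides, HDL-c, glucose, insulin sensitivity, first-phase insulin secretion and total insulin secretion. None is marked as leading.
- **Hypothesis.** There is one, and it spans all nine: "Fucoxanthin modifies components of the metabolic syndrome, insulin sensitivity, and insulin secretion".
- **Specific objectives.** These are written outcome by outcome, for example "Determine and compare WC before and after the intervention with fucoxanthin and placebo", with a separate objective for insulin sensitivity and one for each insulin secretion measure.
- **Sample size.** The Sample section uses a two-sided α of 0.05 and 80% power. Its σ "is the standard deviation of waist circumference (WC), insulin sensitivity, and insulin secretion in" patients with metabolic syndrome, and δ is defined for the same outcomes. The largest resulting size was taken: 28 patients, 14 per arm, including 20% for losses. No outcome is made decisive, and the section does not say which secretion index it means.
- **Analysis.** In the Data collection and statistical analysis plan, the analysis "between groups (independent samples) will be analyzed using the Mann-Whitney U test for quantitative" variables, and a value of p ≤ 0.05 will "be considered statistically significant". Within-arm change is tested at the same threshold. No multiplicity adjustment, testing order, composite or success criterion appears.

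**The concern.** Both the type I error and the power of the trial depend on a rule that the plan does not give. At least four rules fit the text:

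1. any one significant primary supports the hypothesis;
2. all nine must be significant;
3. at least one must be significant in each domain (syndrome components, sensitivity, secretion);
4. each outcome is read alone, with no overall claim.

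Under rule 4, 5% per test is what the plan states. Under rule 1, the error rate is several times that unless the outcomes are very highly correlated. Under rules 2 and 3, error is not inflated when all nine nulls are true, but winning on all nine is much harder than winning on one. Because no rule is fixed, the reading that favours the product can be adopted once the p-values are known.

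**Working it through.** **Inputs from the documents.** Nine primaries (Outcome measures); p ≤ 0.05 for each (statistical analysis plan); two-sided α 0.05 with Z = 1.96, 80% power with Z = 0.842, 14 per arm and a 20% loss allowance (Sample). **Assumed:** one common correlation ρ between outcomes, since the documents give none. Within-arm tests are not counted.

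**The plan's own figure.** N = 28 cannot be reproduced, because σ and δ have no values. It can only be back-solved, as below.

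**Rule 1, any of nine, all nulls true.** If independent: 1 − 0.95⁹ = 0.370. For ρ > 0:

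1 − ∫ [Φ((1.96 − √ρ·x)/√(1−ρ)) − Φ((−1.96 − √ρ·x)/√(1−ρ))]⁹ φ(x) dx

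| ρ | 0 | 0.3 | 0.5 | 0.7 | 0.9 | 0.95 | 0.99 |
|---|---|---|---|---|---|---|---|
| Risk | 37.0% | 32.6% | 26.9% | 20.2% | 12.4% | 9.8% | 6.9% |

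These are normal approximations. With the exact Mann-Whitney test in 40,000 simulated null trials, at ρ = 0, 0.3 and 0.5:
- 14 per arm: 36.6%, 33.1%, 28.4% (size of a single test 4.97%);
- 11 per arm: 35.2%, 31.4%, 27.5% (size 4.73%).

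Holm adjustment in the same runs held the familywise error at 3.7–4.7%.

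**Rule 3, one per domain, all nulls true.** If independent: (1 − 0.95⁶) × 0.05 × (1 − 0.95²) = 0.265 × 0.05 × 0.0975 = 0.0013. At ρ = 0.3 and 0.5 it is 0.5% and 1.2%. This covers the global null only. If the other two domains have real effects, the chance of a false win in a null domain is 26.5% (ρ = 0) or 20.7% (ρ = 0.5) for any of six components, and 9.8% or 9.1% for either secretion index.

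**Rule 2, all nine, power.** Assume each outcome has exactly 80% power. If independent: 0.80⁹ = 0.134. For ρ > 0: ∫ Φ((0.842 + √ρ·x)/√(1−ρ))⁹ φ(x) dx, which gives about 30%, 40%, 51% and 65% at ρ = 0.3, 0.5, 0.7 and 0.9.

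**Price of Holm.** Read the sample-size formula with a plus sign between the Z values (it prints a minus), so d = (1.96 + 0.842)·√(2/n). A size before losses just above 10 per arm (rounded up to 11) gives 2.802 × √(2/10) = 1.25. The upper limit, 14.5/1.2 = 12.08, gives 2.802 × √(2/12.08) = 1.14. Power is from the noncentral t with 2n − 2 degrees of freedom and noncentrality d·√(n/2). Holm's first step uses 0.05/9 = 0.0056, which gives a lower bound for Holm power. Losing 20% of 14 leaves about 11.

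| d | Per arm | At 0.05 | At 0.05/9 |
|---|---|---|---|
| 1.14 | 11 | 72.0% | 36.2% |
| 1.25 | 11 | 79.6% | 45.2% |
| 1.14 | 14 | 82.7% | 50.8% |
| 1.25 | 14 | 88.9% | 61.4% |

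Taken literally with the minus sign, d is 0.46–0.50 and power is about 17–25% unadjusted against 4–6% at 0.05/9. The t-test figures approximate the planned tests.

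**The case against.** The strongest reply is that no sentence says one significant primary is enough. The hypothesis joins three domains, which suggests a joint claim, and the objectives treat each outcome separately. On either reading the 27–37% does not apply. This stands as a limit on the number: it is the error rate of one possible rule, not of the plan as written. It does not supply the missing rule. The two texts point to different rules, and nothing in the analysis plan chooses between them.

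A second reply is that the outcomes are correlated, and unevenly. The sensitivity and secretion indices come from the same glucose tolerance test, and fasting glucose is itself a primary. That is fair, and stopping the headline range at 0.5 is a choice. The risk is still 12% when every pair is correlated at 0.9.

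Third, the low global-null error of the one-per-domain rule can make it look safer than it is. This is correct, and the working shows the error on a truly null domain.

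Fourth, exactly 80% power for all nine is artificial. Only some outcomes were sized, and those that did not set the sample size would have more than 80% on their own assumptions. The 13–65% is therefore illustrative.

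Finally, fixing a rule before unblinding may no longer be possible. The document is dated May 2019 but cites 2021 publications, and parts of the methods are in the past tense. Unblinding status is not stated, so the fix needs a fallback.

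**Conclusion.** The concern holds. The plan has nine unranked primaries, an unadjusted threshold for each, and no rule linking results to the hypothesis. That absence is certain from the text. Its size depends on the rule eventually used:

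- any of nine: 27–37% false-positive risk at assumed correlations of 0.5 to 0, falling to 12% at 0.9 and towards 5% only as correlation approaches 1;
- all nine: no inflation, but power of roughly 13–65% at correlations of 0 to 0.9 if each outcome had exactly 80%;
- each read alone: 5% per test, with no overall claim available.

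All figures assume a common correlation, and the error figures count one between-arm test per outcome. Counting the within-arm tests as support would raise the any-of-nine risk further. This should be corrected, and doing so is cheap.

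**What to change.** Fix the success rule in writing before unblinding. The plan allows for this: "The statistical analysis will be conducted at the end of the total data collection". There are two routes.

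1. **One primary.** The sponsor names one of the outcomes used for sizing (WC, insulin sensitivity, or one stated insulin secretion index) and tests it between arms at two-sided 0.05. The other eight become secondary, reported with estimates and 95% confidence intervals and with no efficacy claim from p ≤ 0.05 alone.
2. **Nine primaries with Holm.** Efficacy is claimed only for the outcomes that remain significant after Holm adjustment across the nine between-arm p-values. Claims are worded outcome by outcome.

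If the data are already unblinded, use route 2 and label it post hoc.

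**Cost.** No extra patients or visits; a wording change if made in time. Route 1 takes confirmatory status from eight outcomes and so narrows the trial's confirmatory question. Route 2 lowers power per outcome. On the plus-sign reading of the formula, the first Holm step has about 36–45% against 72–80% unadjusted with 11 per arm, and 51–61% against 83–89% with 14. Because σ and δ are not given, this loss can only be illustrated; the sponsor should state both so that it can be calculated.
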